9.5 Medical History

Significant medical history should be obtained during the screening visit. All concurrent medical conditions in the last 60 days and any significant medical conditions (e.g., hospitalizations, surgeries, prior medical history) should be collected. Medical history obtained at Screening will include demographic information (e.g., date of birth, gender, race, and ethnicity, etc.), participant's medical history, HIV testing history (CD4 and VL) and HIV medication history, inclusive of prior genotypes (if available). Safety updates will occur at all clinical visits, according to [Appendix 1](#).

During the Step 1 screening period (prior to MGD014 administration), any untoward event that occurs should be collected as a concurrent medical history and not as an AE, unless it is due to a protocol-related procedure. Thereafter (i.e., after the time of study drug administration), any untoward event should be collected as an AE.

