12 ADVERSE EVENT REPORTING AND ASSESSMENT OF SAFETY

The safety assessment will be based on the evaluation of all AEs that occur from the time of initiation of administration of study drug through the End of Treatment Visit or 30 days after the last dose of study drug (whichever is later) and will be determined based on signs, symptoms, physical examination findings, and/or laboratory test results from enrolled participants, as appropriate.

If an AE occurs, the study coordinator, in collaboration with the PI, will evaluate the severity and seriousness of the AE and the relationship to the study drug, and will document the findings.

All adverse events will be graded according to the Division of AIDS Table for Grading the Severity of Adult and Pediatric Adverse Events, corrected Version 2.1, July 2017, which can be found on the DAIDS Regulatory Support Center Web site: <http://rsc.tech-res.com/clinical-research-sites/safety-reporting/daids-grading-tables>.

AEs reported between the time the potential participant signs the informed consent form (ICF) and the administration of the first dose of study drug will be captured as medical history unless the AEs are attributed to protocol-specified procedures that are not part of standard of care that occur during this time period, in which case the AEs will be collected on the Source Document Adverse Event Form. Protocol-related AEs and SAEs will be collected from the time the participant has consented to study participation.

SAEs considered related to study drug may be reported at any time, even after the participant's final treatment visit.

The reporting of laboratory abnormalities as both laboratory findings and AEs should be avoided. Laboratory abnormalities should not be reported as AEs unless any one of the following are met:

- Any criterion for an SAE is fulfilled
- The laboratory abnormality causes the participant to discontinue from the study treatment
- The laboratory abnormality causes the participant to interrupt the study treatment
- The laboratory abnormality causes the participant to modify the dose of study treatment
- The laboratory abnormality requires intervention
- The PI (or designee) determines the laboratory value as an abnormal change from baseline and is of clinical significance for that participant

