12.2 Adverse Event Collection and Documentation

12.2.1 All Adverse Events

Adverse Events (AEs) leading to discontinuation, potential autoimmune events, AEs of \geq Grade 3 severity, related adverse events, and lab abnormalities as well as safety concerns, will be communicated in a timely manner to the UNC IRB, MacroGenics, National Institute of Allergy and Infectious Diseases (NIAID), and FDA per the reporting requirements of each body/authority. The sponsor of this study is MacroGenics. The PI at UNC-CH will be responsible for reporting to MacroGenics, who in turn, will be responsible for reporting to NIAIDs, and FDA per the reporting requirements of each body/authority. AEs occurring after the participant undergoes early termination or completes the trial need not be reported unless the event is serious, and the PI believes that the event may have been caused by the study drug or a protocol procedure.

All participants who receive at least one dose of study drug will be considered evaluable for safety. AEs will be determined based on signs, symptoms, physical examination findings, and/or laboratory test results from enrolled participants as appropriate.

All AEs whether serious or non-serious, will be evaluated from the time a signed and dated ICF is obtained until 30 days following the last dose of study drug. AEs and SAEs reported between the time the participant signs the ICF and the administration of the first dose of study drug will be captured as concurrent medical history unless the events are attributed to protocol-specified procedures. AEs attributed to protocol-specified procedures will be recorded in the database and provided to the sponsor. Additionally, the IRE form will be completed and provided, as appropriate.

All AEs must be reported, regardless of seriousness, severity, or presumed relationship to study drug, must be recorded using medical terminology in the AE source document. AEs will be coded to the Preferred Term using the current version of MedDRA available at study initiation. All records will need to capture:

- The details of the duration, severity, and seriousness of each AE,
- The action taken with respect to the study drug(s),
- The PI attribution/causality assessment concerning the relationship of the AE to study therapy,
- The outcome of the event.

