Visits	1	2	3	4	5	6	7	8	9	10	11
Visit Event	Screen	Enroll ²	Day 0	Day 1	Day 3	Day 14	Day 28	Day 42	Day 49	Day 63	Day 77
Study Weeks	Within 8 weeks of Day 0	0	1	1	2	4	6	7	9	11	
Window period (+ or – days)		≤ 56d screen	≤ 56d screen	0	0	1	1	1	1	3	3
Study Drug Administration											
MGD014 ⁴			X			X	X				
Clinical Procedures											
Informed Consent ¹	X										
Collect Locator information	X										
Assign PID ⁵	X										
Enrollment/Assign SID ⁶		X									
Medical History ⁸	X										
Physical Exam ⁹	X										X
Vital signs ¹⁰	X	X	X	X	X	X	X	X	X	X	
Weight	X	X	X			X	X				
Height	X										
PI review of ART treatment history ¹¹	X										
Directed Physical Assessment ¹²			X	X	X	X	X	X	X	X	
Assess ART and ART adherence ¹³	X	X	X	X	X	X	X	X	X	X	X
Assess venous access	X										
Concomitant Medications ¹⁴	X	X	X	X	X	X	X	X	X	X	
ECG ¹⁵	X		X			X	X				X
Signs, symptoms and diagnosis of illnesses and diseases ¹⁶		X	X	X	X	X	X	X	X	X	X
Pre-Infusion Medications ¹⁷			X			X	X				
Assess for Adverse Events		X	X	X	X	X	X	X	X	X	X
Post-Infusion Assessment ¹⁸			X	X	X	X	X				
Optional Leukapheresis ²³		X						X			

Part 2	Step 1 Pre-Treatment		Step 2 – Treatment					Step 3 – Post Treatment			End of Study ³	
	Visits	1	2	3	4	5	6	7	8	9	10	
Clinical Lab Procedures												
CBC with differential	X	X ²²	X			X	X	X ²²		X	X	
Chemistry Panel ¹⁹	X		X			X	X			X	X	
Calculated Creatinine Clearance	X											
Albumin & Lipase	X									X	X	
Fasting Lipids & Triglycerides	X									X	X	
Pregnancy test (serum) ²⁰	X											
Pregnancy test (urine/POCT) ²⁰			X			X	X			X		
FSH; optional for proof of menopause	X											
PT, INR and aPTT	X										X	
CD4/CD8	X										X	
HIV-1 RNA	X										X	
RPR	X											
Hepatitis B and Hepatitis C	X											
Complete Urinalysis with microscopic exam	X											
Research Laboratory Sample Collection												
HLA		X										
Anti-Drug Antibody (ADA) ²¹	X					X	X				X	
Pharmacokinetics (PK) ²¹			X	X	X	X	X	X			X	
PD: Receptor Occupancy (RO) Measurements ²¹			X	X		X	X				X	
PD: Serum Cytokines ²¹			X	X	X	X	X					
PD: T Cell Phenotype ²¹			X	X		X	X				X	
Resting CD4 T Cell Infection by QVOA ²³		X						X				
Single Copy Assay ²³		X		X				X			X	

1 **Consent:** Obtain prior to obtaining any study-associated procedure.

2 **Study Enrollment:** Determination of study eligibility by the inclusion and exclusion criteria occurs in the Step 1, Visit 1 Screening.

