 - Repeat VS (T, BP, P and RR) with a +/- 5-minute window, may also be captured as necessary to elucidate the course of any untoward event or AE and may be inclusive of all or individual VS components as required to address AE monitoring.
 - Part 1 participants staying in the hospital as an inpatient will have VS assess Q 4 hours with a +/- 5-minute window per hospital unit policy or more frequently as clinically indicated.
 - All other visits: vital signs include T, P, BP, and RR.
- 11 **PI Review of ART History:** if available the most recent HIV-1 genotype should be obtained and presented to PI for review at this time.
- 12 **Directed Physical Assessment:** Guided by review of systems and participant history and addresses any previously identified or new event that the participant experiences since the last study visit or any unresolved signs or symptoms previously experienced.
- 13 **ART and ART adherence:** Non-adherence will be defined as having missed more than 9 total days in the 3 months prior to screening. Assess any missed doses while on study and discussed with Study PI (or designee). Continuance on study will be contingent on adherence.
- 14 **Concomitant medications:** Include all current medications and any as needed (PRN) medications used.
- All medications taken within 4 weeks of study screening.
 - After study entry, record only new over-the-counter, herbal, dietary and vitamin supplements, and prescription medications. Mark any discontinued medications.

c. Document all doses of MGD014 treatments and permanent discontinuation.

15 ECG: Perform in triplicate (approximately 1 minute apart).

a. Screening Visit:

- a. Part 1; Performed within 28 days of the first dose of MGD014.
- b. Part 2: Performed within 56 days of the first dose of MGD014.

b. Infusion Visits: pre-infusion (within 30 min), end of infusion (within 30 min of the End of Infusion (EOI), 1 hour after the EOI (+/- 5 minutes after EOI).

c. End of Study Visit

16 Signs and Symptoms and Diagnosis:

- a. Screening: record all diagnosis and disease, record all graded baseline labs, signs and symptoms that occurred within 28 days of screening. Untoward events due to protocol-related procedures should be recorded as AEs.
- b. After study entry: Record all AEs related to study drug product regardless of grade.

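### Appendix 1 footnote 16b ties AE recording after study entry to drug relatedness, against Sections 9.5, 12, 12.1.1 and 12.2, so some non-serious events rated unrelated could be missing from the safety tables

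*Protocol*

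**What the plan says.** Footnote 16 of Protocol Appendix 1 belongs to the schedule row "Signs, symptoms and diagnosis of illnesses and diseases", which runs from enrolment to the end-of-study visit in both parts. Part (a) covers screening. Part (b) is the instruction for everything afterwards: "After study entry: Record all AEs related to study drug product regardless of grade". A separate row, "Assess for Adverse Events", carries no footnote.

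The body of the protocol sets a different rule. Section 12.2.1 states: "All AEs must be reported, regardless of seriousness, severity, or presumed relationship to study drug". Section 9.5 states: "Thereafter (i.e., after the time of study drug administration), any untoward event should be collected as an AE". Section 12 opens with: "The safety assessment will be based on the evaluation of all AEs that occur from the time of initiation of administration of study drug". Section 12.1.1 defines an AE without reference to causality, and Sections 12.2.4 and 12.2.6 require all AEs in the database and in the source documents. Under Section 12.1.4 the principal investigator assigns causality, and Unlikely and Not related both count as not related.

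SAP 4.8.1 plans a table of all AEs and a separate table of all study drug-related AEs.

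**The concern.** Safety and tolerability is the primary objective, and the AE tables are its main output. They are only as complete as what the site records. Footnote 16b turns causality from an attribute of a recorded event into a condition for recording it. In a single-site, open-label trial where the principal investigator makes the causality call, full capture is what lets someone else question that call later. If a mild or moderate non-serious event recurs across participants and is rated Unlikely each time, the pattern shows only if each occurrence is in the database.

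The schedule is also a working document. Section 9.5 itself refers staff to Appendix 1 for the safety updates at each clinical visit, so the footnote is likely to be read.

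**Working it through.** No calculation in the plan bears on this point. The check is a comparison of the recording rules, followed by a trace of which events are exposed.

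**1. The rules side by side**

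| Place | What is covered | Limited by causality? |
|---|---|---|
| Protocol 9.5 | Any untoward event after dosing | No |
| Protocol 12 | Safety assessed on all AEs from first administration | No |
| Protocol 12.1.1 | AE definition | No |
| Protocol 12.2.1 | All AEs, whatever the seriousness, severity or relationship | No |
| Protocol 12.2.4 | All AEs in the database | No |
| Protocol 12.2.6 | All AEs in source and database | No |
| Appendix 1, footnote 16b | AEs related to study drug, any grade | **Yes** |

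Footnote 16b stands alone. Section 9 describes Appendix 1 as giving the timing of procedures, but nothing says that the body text overrides a footnote.

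**2. Which events are exposed**

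Several kinds of event are captured whatever their causality:
- SAEs, Grade 2 or higher CRS or IRR, AEs leading to permanent discontinuation of study drug, and COVID-19 (Section 12.2.2 and Table 2).
- Grade 3 and 4 laboratory findings (Sections 12 and 12.2.1).
- Section 12.2.1 also names AEs of Grade 3 or higher for timely communication, although the corresponding text in 12.2.6 is confined to those related to MGD014.

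What remains is mainly non-serious clinical events of lower grade, rated Unlikely or Not related, that do not end dosing. Table 2 gives these one route, the Adverse Event Form.

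**3. Where an omission would show**

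- *SAP 4.8.1.* The All AEs tables would lose these events; the study drug-related tables would not.
- *Protocol 14.9, monthly review.* This reassesses the relationship of reported events. An unrecorded event is not available to it.
- *DLTs (Section 4.4) and the 14.9 suspension triggers.* DLTs are defined on drug-related AEs. The Grade 3 or higher trigger counts possibly, probably or definitely related toxicities, and the other trigger counts DLTs. Footnote 16b keeps related events, so these counts do not change directly.

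**4. Scale**

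The SAP tables count participants with at least one event. If one participant's only AE is unrecorded, the percentage for that group changes by 1/n:
- n = 3 (a standard cohort from 3 to 8): 1/3 = 33 points.
- n = 6 (an expanded cohort, or Part 2 if full): 1/6 = 17 points.
- n = 26 (approximate planned total): 1/26 = 4 points.

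The same arithmetic applies to a single preferred-term row when a participant's only occurrence of that term is unrecorded. The documents do not say what share of AEs will be rated unrelated, so an expected loss cannot be calculated.

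**The case against.** The strongest reply is that the protocol already settles the matter. The rule to record everything is stated repeatedly and explicitly in Sections 9.5 and 12. The AE row of the schedule has no restriction. Footnotes 12 and 18 direct staff to any new event and to any potential treatment-emergent event. Section 12.1.4 asks the investigator to name the likely cause of events rated unlikely or unrelated, which presupposes that they are recorded. Footnote 16b does not contain the word *only*, although footnote 14 in the same appendix does, so 16b may have been meant to stress that grade is no filter.

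Most of this stands, and it is why the loss is a risk and not an expectation. It does not remove the conflict. The reference to relatedness in 16b is a restriction that no other recording rule has, and a reader of the schedule is not told to disregard it.

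A reader might infer more than the documents support:
- *The two SAP tables would become identical.* They would not, because the categories in step 2 of the working are captured whatever their causality.
- *The All AEs figure would fall by the share of events rated unrelated.* The tables count participants, and a participant with any other recorded AE still counts in the overall row.
- *Dose escalation or stopping counts would be distorted.* They rest on related events, which 16b keeps. A wrong causality rating is a separate matter.
- *Omitted events would be lost for good.* Section 15.1 keeps clinical notes as source and provides for independent monitoring.

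**Conclusion.** The contradiction is clear from the text and should be corrected. Followed literally, footnote 16b could keep non-serious events rated Unlikely or Not related out of the All AEs tables and out of the monthly relatedness review. Whether that happens depends on a coordinator applying the footnote in preference to Section 12.2.1, and nothing in the documents shows that anyone has done so. The possible effect is visible at cohort level because the cohorts are small, but its expected size is unknown. This is an inconsistency in an operational instruction that feeds the primary safety output. It is not a flaw in the design or in the escalation rules.

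**What to change.** Replace footnote 16b with wording to this effect: *From the first administration of study drug, record every AE whatever its seriousness, severity or causality rating, following Section 12.2.1 including its rules for laboratory findings, and record causality as in Section 12.1.4. Before the first administration, record events as medical history unless a protocol procedure caused them, as in Sections 9.5 and 12.2.1.*

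Two details matter. The rule should start at first dosing and not at study entry, because events before dosing are otherwise medical history. It should also carry the laboratory rules of 12.2.1, because Grade 1 and 2 laboratory findings generally need not be reported as AEs, and a bare instruction to ignore grade would create a new conflict.

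Attach the same footnote to the AE assessment row. Section 2.4.3 refers to participants through Cohort 8, so people have already been dosed. For them, confirm during routine source review before database lock that unrelated-rated AEs were entered.

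The cost is one footnote in an amendment, a few extra AE entries, and a short source check in a study of about 26 participants.

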2.4.4 Every 2 Week Administration

For the multi-dose expansion cohort in Part 2, MGD014 at 300 mcg/kg will be administered IV Q2W for a total of three doses over 4 weeks. The Q2W administration of MGD014 is supported by the repeat-dose toxicology study in cynomolgus monkeys (Study 20093423) in which MGD014 was administered weekly for 6 weeks by 2-hour IV infusions. Simulations based on the allometric modeling of the cynomolgus monkey PK data predicts that the concentration profiles in human participants will reach steady-state between the third and fourth dosing intervals and that the accumulation factor for exposure following the last (sixth) dose will be 1.84.

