3.2 Secondary Objectives

- Assessment of PK and immunogenicity (ADA) of MGD014.
- Assessment of serum cytokine levels following MGD014 administration.

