4.3 Multi-Dose Cohort Expansion Phase (Part 2)

Part 2 is a multi-dose expansion cohort with repeat administrations of MGD014 at 300 mcg/kg; see Study Part 2 Schema, **Figure 5**. Up to 6 patients will be enrolled in Part 2.

Participants previously enrolled in and having completed Part 1 may be considered for enrollment in Part 2, provided they continue to meet all eligibility criteria, did not experience any DLT in Part 1, and do not have any detectable ADA at the completion of Part 1.

In Part 2, additional optional assessments on the effects of MGD014 on HIV latent infection parameters include measurements of resting cell infection (frequency of persistent infection of resting CD4 T cells) by QVOA, SCA, and T-cell phenotype and functional properties.

Figure 5 Part 2: Dose Expansion Study Schema

(a) Screening, eligibility and optional baseline leukapheresis (b) optional leukapheresis post-treatment for frequency of persistent infection of resting CD4 T cells.

Abbreviations: ADA = anti-drug antibody; ART = antiretroviral therapy; leuk = leukapheresis; PK = pharmacokinetics; QVOA = quantitative viral outgrowth assay.

Step 1 Optional Baseline Leukapheresis: After obtaining the informed consent and confirmation that the participant qualifies for the study, the participant enrolls in the study. If the participant gives consent, an optional baseline leukapheresis is completed. The resting CD4 T cells obtained in the leukapheresis will determine the baseline frequency of resting CD4 T-cell infection. Additionally, baseline measurements at 2 independent, pre-MGD014 time points will determine baseline T-cell function and SCA levels. Note: if the frequency of resting CD4 T cell infection is ≤ 0.3 infected cells per million (IUPM), as measured by QVOA, a further decrease from this low frequency of infection cannot be definitively measured given the QVOA assay threshold and variance [51].

Step 2 Treatment phase: Eligible participants will continue their ART regimen and receive 3 infusions of MGD014 at the dose of 300 mcg/kg. Participants are monitored for 6 hours on site following their first infusion. Participants will be monitored for 4 hours on site following subsequent infusions. Clinical and laboratory parameters for safety, including clinical assessment

of cytokine release, will be assessed after each MGD014 infusion. PK and PD data will be collected, and serial blood draws will be obtained to assess the impact on T cell functional properties.

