Note: Actual start and end of infusion times, PK, and ADA sample collection times will be recorded on the source documents. All sample time points are hours after EOI, unless otherwise specified. Samples required at EOI can be drawn up to 5 minutes before the infusion is complete, post EOI samples can be drawn +/- 5 minutes; duration of infusion = 120 minutes. 24 - and 48-hour samples will be drawn on Day 1 and 2 respectively.

Abbreviations: ADA = Anti-drug antibody; EOI = end of infusion; PK = Pharmacokinetic.

PART 2 Pharmacokinetics, Immunogenicity, and Pharmacodynamic Biomarkers Blood Sampling Schedule for MGD014						
MGD014 Dosing	Treatment Day	PK ^a Sampling Time (Hours)	ADA Sampling Time (Hours)	Receptor Occupancy ^b (Hours)	Serum Cytokines ^c (Hours)	T cell Phenotype (Hours)
X	0	0 ^d (Pre-infusion)		0 ^d (Pre-infusion)	0 ^d (Pre-infusion)	0 ^d (Pre-infusion)
	0	EOI				
	0	1 (post EOI)				
	0	4 (post EOI)		4 (post EOI)	4 (post EOI)	4 (post EOI)
	1	24 +/- 5 hours (post EOI)		24 +/- 5 hours (post EOI)	24 +/- 5 hours (post EOI)	24 +/- 5 hours (post EOI)
	3	72 +/- 5 hours (post EOI)			72 +/- 5 hours (post EOI)	
X	14	0 (Pre-infusion)	0 (Pre-infusion)	0 (Pre-infusion)		0 (Pre-infusion)
	14	EOI		4 (post EOI)	4 (post EOI)	4 (post EOI)
X	28	0 (Pre-infusion)	0 (Pre-infusion)	0 (Pre-infusion)		0 (Pre-infusion)
	28	EOI		4 (post EOI)	4 (post EOI)	4 (post EOI)
	42	1008 hours +/- 1 day				
	77 (EOS visit)	1848 hours +/- 3 days	X	X		X

- a Do not collect PK samples from infusion port. Obtain PK samples as follows: Pre-infusion: Before start of infusion on visit day (dosing day) or day before. When collecting multiple samples, collect the PK sample first.
- b If at any time in Step 3 RO reaches below the limit of detection, at the discretion of the PI or designee, further measurement of RO may be deemed unnecessary.
- c Additional samples may be obtained selectively at additional time points in participants who experience signs and symptoms of cytokine release.
- d All pre-dose PK, ADA, Receptor Occupancy including T-cell binding, cytokines, and T-cell Phenotype samples will be collected prior to start of MGD014 infusion; the start of MGD014 infusion is designated as time = 0 hour.

Abbreviations: ADA = Anti-drug antibody; EOI = end of infusion; PK = Pharmacokinetic.

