4.11 Pharmacodynamic Endpoints and Analyses

Summary statistics for biomarkers, such as but not limited to those listed under **CP-MGD014-01 Protocol Section 10.3** and corresponding changes from baseline, will be summarized and may also be presented graphically as will possible associations between changes in PD measures of interest and MGD014 dose and exposure.

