4.11.1 Serum Cytokines

Data will be tabulated and summarized by dose panel and time. Plots of serum cytokine levels versus time may be provided. Additional analyses may be conducted in order to characterize the relationship between the MGD014 serum concentrations and serum cytokines (e.g., an exposure-response analysis), if deemed appropriate.

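### Part 2 schedules no pre-infusion serum cytokine sample at infusions 2 and 3, so two of three infusions lack a same-infusion before/after pair for a secondary objective

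*Protocol*

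**What the plan says.** Protocol 3.2 lists "Assessment of serum cytokine levels following MGD014 administration" as a secondary objective, and SAP 2.2 repeats it. For Part 2, Protocol 2.4.4 states that "MGD014 at 300 mcg/kg will be administered IV Q2W for a total of three doses over 4 weeks", and Protocol 4.3 that "Up to 6 patients will be enrolled in Part 2".

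Appendix 1 (Part 2) marks serum cytokines on Days 0, 1, 3, 14 and 28 and refers to Appendix 2 for the detailed times. Two footnotes to the Part 2 table in Appendix 2 bear on cytokines:

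- Footnote c allows extra cytokine samples, selectively, in participants with signs and symptoms of cytokine release.
- Footnote d states that "All pre-dose PK, ADA, Receptor Occupancy including T-cell binding, cytokines, and T-cell Phenotype samples will be collected prior to start of MGD014 infusion".

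On analysis, SAP 4.11.1 says of cytokines that "Data will be tabulated and summarized by dose panel and time". It leaves an exposure-response analysis optional. SAP 4.11 says of PD biomarkers generally that "corresponding changes from baseline, will be summarized". It does not say whether baseline means Day 0 or the value before each infusion.

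**The concern.** Part 1 already describes cytokines after a single dose. What Part 2 adds is repeat dosing, so the cytokine readings at infusions 2 and 3 are the new information on this objective. Each of those infusions has one scheduled reading, 4 h after the end of infusion, and no value from just before it.

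If a participant's 4 h value on Day 14 or Day 28 is above the Day 0 value, the scheduled cytokine data do not show whether it rose after that infusion or was already raised beforehand. An earlier rise could be carry-over from the previous dose, drift since Day 0, or an intercurrent illness. In at most six people, one or two such values could shape the description of repeat dosing in either direction.

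**Working it through.** There is no sample size, power or precision figure for cytokines to reproduce. The check is a reading of the Part 2 table in Appendix 2, followed by a count.

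**Step 1. Cells in the table** (yes = a sample is scheduled)

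| Row | PK | ADA | RO | Cytokines | T-cell phenotype |
|---|---|---|---|---|---|
| Day 0 pre-infusion | yes | blank | yes | yes | yes |
| Day 0, 4 h | yes | blank | yes | yes | yes |
| Day 1, 24 h | yes | blank | yes | yes | yes |
| Day 3, 72 h | yes | blank | blank | yes | blank |
| Day 14 pre-infusion | yes | yes | yes | **blank** | yes |
| Day 14 post-infusion | EOI | blank | 4 h | 4 h | 4 h |
| Day 28 pre-infusion | yes | yes | yes | **blank** | yes |
| Day 28 post-infusion | EOI | blank | 4 h | 4 h | 4 h |

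(The Day 0 EOI and 1 h rows hold PK only. Neither Day 42 nor Day 77 has a cytokine entry.)

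The blank is identical on Days 14 and 28 and the neighbouring columns align, so a fault in reading the table is unlikely. Appendix 1 agrees with this layout: ADA is marked on Days 14 and 28 but not Day 0.

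**Step 2. Do the footnotes supply the missing sample?** Footnote c does not: it is selective, applies to participants with symptoms of cytokine release, and is not a scheduled pre-infusion sample. Footnote d does not either. Its marker is on Day 0 cells only, and it states when pre-dose samples are taken. It also names ADA, although the Day 0 ADA cell is blank, so being listed there does not create a sample.

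**Step 3. Count per participant**

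- Infusion 1: 1 pre + 3 post
- Infusion 2: 0 pre + 1 post
- Infusion 3: 0 pre + 1 post
- Total: 4 + 1 + 1 = 6 samples
- Infusions without a same-infusion pair: 2/3 = 66.7%

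With six participants there are 6 × 3 = 18 infusions, of which 6 × 2 = 12 lack a pair and 6 have one. RO and T-cell phenotype have a pre/4 h pair at all three infusions, so among these markers the gap is specific to cytokines.

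**Step 4. Both parts together.** Every Part 1 infusion has a pre-infusion cytokine sample. With the minimum of 20 Part 1 infusions, (20 + 6)/(20 + 18) = 26 of 38 infusions have a pair. All 12 without one are repeat doses.

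**Step 5. After the change.** Samples per participant rise from 6 to 8 (36 to 48 for six participants), and paired infusions rise from 6/18 to 18/18.

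**The case against.** The strongest reply is that nothing planned depends on the missing samples. The objective concerns levels after administration, and a post-infusion level exists for all three infusions. Tabulation by dose panel and time can be done as scheduled, and the Day 0 pre-infusion value gives a change from baseline at Days 14 and 28. This stands. The gap limits interpretation and breaks no stated analysis.

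Other data also help. Part 1 follows cytokines at 4 h, 24 h, 48 h and Day 7, including at 300 mcg/kg, which informs persistence after one dose. Part 2 has pre-infusion T-cell phenotype on Days 14 and 28, and adverse event review, vital signs and concomitant medications at both visits. These reduce the ambiguity, but none is a cytokine value from just before the infusion.

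Three stronger readings are tempting and are not supported:

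- **Day 0 is an invalid baseline because drug is still on board.** The protocol's projections stop at the 7-day trough (Table 1: 802.6 ng/mL at 300 mcg/kg), so pre-dose values at Days 14 and 28 need assumptions. Take KD = 6.9 nM × 111.8 kDa = 771 ng/mL, which reproduces Table 1: 802.6/(802.6 + 771) = 51.0%. For an assumed half-life h in days, the Day 14 level is C14 = 802.6 × 2^(−7/h) and the Day 28 level is C14 × (1 + 2^(−14/h)). The 8-day half-life in Protocol 4.5 gives about 438 and 568 ng/mL, or 36% and 42% occupancy. The 1.84 accumulation factor in 2.4.4, read with one compartment, implies h of about 6.2 days if dosing is weekly or 12.4 days if every two weeks. The ranges are then about 32–41% before infusion 2 and 36–51% before infusion 3. Even so, occupancy is not evidence of a shifted cytokine baseline: Protocol 2.2.2 reports no noteworthy cytokine increase in monkeys, including at maximal CD3 binding.
- **A planned exposure-response analysis is confounded.** That analysis is optional, and it relates concentration to cytokine level without requiring an infusion-specific change.
- **Cytokines go unmeasured from Day 14 to the end of the study.** Day 28 has a 4 h sample. It is only after Day 28 that none is scheduled.

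**Conclusion.** The gap is real and modest. As scheduled, 2 of 3 Part 2 infusions per participant have no same-infusion cytokine pair. The figure of 12 of 18 is a maximum, because enrolment is up to six. The conclusion rests on the blank Day 14 and Day 28 cells, and on reading footnote d as a statement of timing. If the sponsor meant footnote d to require these samples, the table still needs correcting to say so.

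A reader might infer that infusions 2 and 3 have no baseline at all, or that the schedule contradicts the SAP. Neither follows: the Day 0 value is available, and the SAP asks for no per-infusion change. What is lost is part of the ability to attribute a raised 4 h value to the infusion just given. No hypothesis test, dose decision or primary-objective conclusion has been shown to depend on it. The change is worth making mainly because it is cheap.

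**What to change.** In the Part 2 table of Appendix 2, add a time-0 pre-infusion entry to the Serum Cytokines column for Days 14 and 28, and extend the footnote d marker to those cells. In SAP 4.11.1, report the 4 h value minus the same day's pre-infusion value for each infusion, alongside the change from the Day 0 pre-infusion value, and state which baseline each summary uses.

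Cost: two extra serum aliquots per participant, at most 12 in total, with the matching assay wells and one extra table column. Pre-infusion blood is already drawn on both days, and Protocol 9.16 has PK, ADA and cytokine samples processed at the same laboratory core, so no new visit or needle-stick is needed.
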